#### (vi) Observations and measurements

Based on work performed in prior studies, we do not anticipate biomarker responses that would suggest adverse reactions to Meriva (1-4). We will therefore not collect blood samples during the 6 week treatment with Meriva to monitor adverse biomarker responses. Research blood will be collected at baseline during the last week of XRT or up to three months post XRT and at the conclusion of the 6 weeks treatment with Meriva. Patients will be interviewed weekly by phone to ensure they are not experiencing side effects previously described for curcumin, including nausea and diarrhea. If they do report worsening of these symptoms compared to before they started Meriva, they will be asked to immediately discontinue taking Meriva and come to the clinic for full physical evaluation. In the case that a patient experiences adverse side effects and stops taking Meriva, self-report information and blood samples will still be collected at the early termination visit.

#### Curcumin Visit I: Screening

- Information regarding disease characteristics (including stage, tumor size, grade)
- Patient demographics (including age, race, co-morbidities, social history)
- Systemic treatment (including hormone therapy, systemic therapy), surgical treatment, and radiation treatment will be collected and recorded.
- Informed consent process
- Physician or NP evaluation or modified physical
- CBC with diff
- Serum quantitative pregnancy test
- Urinalysis with microscopy
- Self-report of fatigue level and pain on a scale of 0-10, 0 being none and 10 being extreme. The patient's self-report of fatigue at these visits will be used to assess the grade of their fatigue.
- Inventory of Depressive Symptomatology – Self Reported (IDS-SR)[41]- Participants with an IDS score > 32 or a score of 2 or higher on IDS item #18 will be referred to [name]
- PROMIS Fatigue Short form [49]
- Patient reimbursement
- Review labs for infection and anemia

#### Curcumin Visit II: Baseline (XRT end – last week of XRT or within 3 months after)

- Inclusion criteria completed

[figure not shown]
- Mediterranean diet survey, Inventory of Depressive Symptomatology – Self Reported (IDS-SR)[41], Pittsburgh Sleep Quality Index (PSQI) [42-45], Perceived Stress Scale (PSS)[46], Godin Leisure-Time Exercise Questionnaire (GLTEQ)[48], Multidimensional Fatigue Index (MFI) (36) and PROMIS Fatigue Short form [49]
- Self-report of fatigue level and pain on a scale of 0-10, 0 being none and 10 being extreme.
- Fasting blood draw for research (two 4 ml purple tops, two 6 ml purple tops, and 1 tempus tube)
- Ultrasound scan and photographs at PI's discretion
- Randomization
- Dispense medications and medication diary
- Patient reimbursement

**Compliance:**

Patients will be asked to fill out a medication diary daily and report any missed doses during weekly telephone interviews. Patients who report taking less than 75% of their medication between interviews may be excluded from study participation at PI's discretion.

**Curcumin Visit III:** final evaluation of the last week of Meriva or placebo treatment

- Physician or NP evaluation or modified physical

- CBC with diff– review for infection and anemia
- Fasting blood draw for research ( two 4 ml purple tops, two 6 ml purple tops, and 1 tempus tube)
- Ultrasound scan and photographs at PI’s discretion
- Self-report of fatigue level and pain on a scale of 0-10, 0 being none and 10 being extreme.
- Inventory of Depressive Symptomatology – Self Reported (IDS- SR)[41], Pittsburgh Sleep Quality Index (PSQI)[42-45], Perceived Stress Scale (PSS)[46], Godin Leisure-Time Exercise Questionnaire (GLTEQ)[48], Multidimensional Fatigue Index (MFI) (36) and PROMIS Fatigue Short form [49]
- Collect unused medications and medication diary
- Patient reimbursement

During the screening visit Curcumin Visit 1, a urinalysis, CBC with differential, serum quantitative pregnancy test, and physician evaluation or modified physical by the study NP will be performed. A subset of patients may have an ultrasound scan and photographs done by Radiation-Oncology research team. The lab tests will be processed in the Emory Medical Laboratory (EML) system. The results of the evaluation or modified physical and urinalysis as well as the CBC with differential will be reviewed to rule out infection or anemia to verify eligibility. If infection or anemia or pregnancy is detected, the patient will be withdrawn from the study.

An ultrasound of the treated breast or chest wall and untreated breast and axilla may be performed at the baseline and final evaluation visits to assess cutaneous toxicity. These scans will be conducted based on the availability of research staff and space to conduct the scan. Each scan will take between 5 and 10 minutes to perform. Photographs of the treated breast (or chest wall) as well as the contralateral breast will also be taken. Ultrasound data and photographs will be stored in a computer for later review.

The patient will be randomized to Meriva or placebo at Curcumin Visit II. Medications will be dispensed, to be started the following Monday. A physician evaluation or modified physical will also be performed at the final evaluation, Curcumin Visit III. A physical exam will be performed at the time of early termination as well as a CBC with differential, research bloods, and self-report forms.

For safety precaution, patient will be asked to repeat Curcumin Visit I if a lapse of 30 days or greater occurs between Curcumin Visit I and Curcumin Visit II.

See checklist below for details on Curcumin Study Visits. **Laboratory Measures**

#### **Sample Collection & Handling**

Blood will be collected using purple top vacutainers (containing EDTA additive) and a tempus tube. The blood volume per tube will be 3 – 3.5 ml for the 4 ml tubes, and 5 – 5.5 ml for the 6 ml tubes. Four purple top tubes and a tempus tube will be collected at baseline and at the final evaluation under fasting conditions. Prior to collection, study numbers will be determined and barcoded labels will be placed on collection aliquots.

Meriva for Treatment-induced Inflammation and Fatigue in Women With Breast Cancer  
**IRB#00055328**

Curcumin Study Checklist										
	CLINIC VISIT	CLINIC VISIT	CLINIC VISIT						CLINIC VISIT	CLINIC VISIT
Procedure	Initial Meeting	Visit I Screening	Visit II Baseline	Tx wk 1 Call	Tx wk 2 Call	Tx wk 3 Call	Tx wk 4 Call	Tx wk 5 Call	Visit III	Early Termination
Curcumin ICF for review	x									
Curcumin Consent		x								
Inclusion Criteria		x								
Demo Sheet		x								
Physician/NP Evaluation		x							x	
Physical Examination										x
Urinalysis		x								
Serum quantitative pregnancy		x								
CBC w/diff		x							x	x
Review labs for infection and anemia		x							x	x
Blood draw for research: 4 purple tops and 1 tempus			**						**	**
Randomize/dispense meds			***							
Patient reimbursement		x	x						x	x
Phone Interview				*	*	*	*	*		
Meds returned/counted									x	x
Meds diary returned									x	x
Concomitant Medications reviewed		x	x	x	x	x	x	x	x	x
Adverse Events Reviewed				x	x	x	x	x	x	x
Ultrasound scan and photographs			x						x	
Fatigue Level		x	x						x	x
Pain Level		x	x						x	x
Mediterranean Diet Survey			x							
GLTEQ			x						x	x
MFI 20			x						x	x
PSS			x						x	x
IDS-SR		x	x						x	x
PSQI			x						x	x
PROMIS		x	x						x	x
* Weekly phone interviews for Adverse Event Assessment/ Medication Compliance. If indicated, stop medications and come in for physical exam.										
** Plasma analysis of inflammatory markers, PBMC analysis of NF-kB DNA binding, and gene expression.										
*** Medication dispensed during treatment check by physician or nurse practitioner. Medication to begin the following Monday after medications are dispensed.										
v. 12/19/2017										

Blood samples will be drawn at the same time of day between 9:00-11:00 am (to reduce potential circadian effects) under sterile conditions at each of these visits. Whole blood for plasma, buffy coat, and peripheral blood mononuclear cells (PBMCs) will be collected into EDTA vacutainer tubes. Two tubes will be stored at 4°C for less than 45 minutes, after which plasma and buffy coat will be separated by centrifugation at 1000 x g for 10 minutes at 4°C, aliquoted into siliconized polypropylene tubes and stored at -80°C until assayed. Two tubes will be kept at room temperature for less than 45 minutes, after which plasma will be replaced

by saline for the isolation of PBMCs using density gradient centrifugation. PBMCs will be stored in freezing serum (90% fetal bovine serum, 10% DMSO) at -80°C until nuclear extraction or mRNA isolation.

#### Plasma Analysis of Inflammatory Markers

Plasma concentrations of TNF alpha, sTNFR2, IL-1ra, and IL-6 will be determined using sandwich ELISA according to manufacturer's protocol (R & D Systems, Minneapolis, MN). Each determination (excluding the soluble cytokine receptors which require less sample) requires 100-150µl of sample, and all samples will be assayed in duplicate. ELISA assays will be performed in [name] laboratory. Quality control plasma of both low and high cytokine concentrations will be included with every assay. The mean inter- and intra-assay coefficients of variation for control samples are reliably 10% or less. High sensitivity CRP will be measured in the CLIA certified laboratory of the Emory University Hospital using a standard turbidimetric assay.

#### NF-κB DNA Binding

Peripheral blood mononuclear cells (PBMC) will be isolated on ficoll-hypaque gradients before nuclear protein extraction and DNA-binding analysis. DNA-binding of NF-κB will be determined by an ELISA kit as previously described by our group (Active Motif [Carlsbad, CA])(37, 38). Like electrophoretic shift assays (EMSA), the enzyme-linked immunosorbent assay (ELISA)-based method measures transcription factor binding to their consensus DNA sequences. The ELISA-based approach detects DNA-protein interaction by observing transcription factor consensus sequence binding in a 96-well plate. The consensus sequence is fixed to the bottom of the well and specificity is demonstrated by adding a soluble consensus sequence to control wells. We have demonstrated that the ELISA-based approach has high sensitivity and specificity for detecting activated transcription factors by running nuclear extracts in both EMSA and DNA-binding ELISA with the same effects observed (39).

#### Gene Expression

RNA will be isolated from PBMCs collected as described above using an RNeasy Mini Kit (Qiagen, Hilden, Germany). The A260/A280 ratio will be used to assess RNA purity. Samples will be analyzed in the Biomarker Profiling Core at The Emory Winship Cancer Institute for gene expression analysis using an Illumina platform. Initial data analysis will be conducted using the BeadStudio software from Illumina, and the data will then be exported to the TELiS system available online (40). The TELiS database in conjunction with the PromoterStats statistical tool will be used to identify transcription factors (i.e. NF-κB) driving gene expression detected in the microarray. Of note, previous studies using the TELiS database have identified profiles of gene expression that reflect NF-κB signaling activity (40).

#### Microarray Analysis

Specimens collected in Tempus tubes will be used for microarray analysis. 2-8µg of high quality RNA may be extracted per 1mL of blood. Tempus tubes contain up to 4mL of blood,

and therefore at least 8µg of RNA will be extracted for analysis and validation. RNA will be molecularly characterized using an Illumina BeadStation and will be run on the HumanHT-12 Beadchips or a comparable chip. Specimens will have RNA extracted for expression profiling in a batched manner to allow for minimal variation in extraction, in vitro transcription (IVT) labeling, and hybridization to the Beadchips. The primary endpoint of the microarray data analysis will be to determine if genes regulated by NF-kB exhibit decreased expression when patients are treated with Meriva vs. placebo.

### Outcome Measures

The primary outcome to be measured will be the change in NF-kB DNA binding and its downstream mediators (plasma concentrations of TNF-alpha, sTNFR2, IL-1ra, IL-6 and CRP) after six weeks of treatment with daily placebo or Meriva. The secondary endpoint will be the change in fatigue from baseline to six weeks after treatment with Meriva or placebo. . Microarray analysis will also be performed before and after treatment to look at the expression of NF-kB response genes: **Primary Hypothesis: Patients responsive to Meriva will have decreased NF-kB DNA binding, decreased activation of NF-kB responsive genes and decreased downstream mediators of NF-kB pathway activation.**

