**The primary objective of this protocol is to determine if Meriva reduces NF-kB DNA-binding and its downstream mediators in patients receiving XRT for their breast cancer after having completed chemotherapy.** Patients who have received prior chemotherapy will be eligible, because we have found that this enriched population is at particular risk for exhibiting increased NF-kB DNA binding following XRT. NF-kB DNA-binding is a direct measure of NF-kB pathway activity, while plasma concentrations of TNF-alpha and its soluble receptor sTNFR2, interleukin (IL)-1 receptor antagonist (IL-1ra), and C-reactive protein (CRP) are downstream indicators of NF-kB activity.

Secondary objectives will be to 1) determine if Meriva decreases levels of fatigue as measured by the Multidimensional Fatigue Inventory (MFI) in BRCA patients, and 2) determine longitudinal variances in skin changes measured by ultrasound in breast cancer patients undergoing XRT. Results from this study will contribute to the limited research available on the capacity of Meriva and curcumin to inhibit NF-kB and its downstream mediators in vivo.

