#### (iv) Design

This double-blind, placebo controlled, randomized clinical trial will enroll BrCA patients seen at the Emory Breast Centers (Winship Cancer Institute of Emory University and Emory University Hospital Midtown) or in the community for XRT who were previously treated with chemotherapy. These patients will be approached for enrollment on this therapeutic study during the first three weeks of receiving radiation therapy or one to three months post XRT.

In patients previously treated with chemotherapy, we will administer placebo or Meriva daily for approximately 6 weeks, beginning immediately after the completion of XRT or up to 3 months post-XRT. Patients will be randomized to placebo or Meriva-500 (500 mg PO BID) using a computerized system under the control of Emory Pharmacy. Randomization will occur in blocks of 10. Meriva-500 will be obtained from Thorne Research. Blood will be drawn at baseline and at the first follow-up appointment to determine NF-kB DNA-binding in peripheral blood mononuclear cells, expression of NF-kB regulated genes, and plasma cytokine concentrations. The final study visit will occur during the 6 week treatment period. Study Coordinator will make an effort to coincide the follow up visit and six week post-radiation follow up visit. Because placebo or Meriva is being given after XRT is complete, it is unlikely to alter the efficacy of the XRT or enhance side effects of XRT.

Thirty patients will be enrolled per arm. NF-kB DNA-binding, downstream mediators of NF-kB activity and microarray analysis of NF-kB regulated genes will be used to determine NF-kB pathway activation. If any of these measures of NF-kB DNA binding activity (the primary outcome variables)

**Patients will receive daily Meriva treatment for approximately 6 weeks beginning immediately after radiation therapy (XRT) or up to 3 months post-XRT. Peripheral blood will be drawn during the last week of XRT and again after 6 weeks of Meriva (or Placebo) for assessment of NF-kB pathway activation.**

decrease to the mean level of non-chemotherapy treated women who receive XRT, the 500 mg BID dose level will be considered successful.

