**(v) Dosing**

The 500 mg BID dose of Meriva that will be used in this protocol was selected after consulting with [name], DVM, Head of Business Development at Indena S.p.A (Milan, Italy) and [name], Chief Scientific Advisor, Indena S.p.A (Milan, Italy). The dose proposed for use here is similar to doses used in other studies investigating Meriva (1-4). For example, the single dose selection is also supported by a recent study by Cuomo and colleagues showing that 200-300 mg of curcumin as Meriva (i.e. a single Meriva dose of 1000-1500 mg) resulted in 29-fold higher for Meriva than for its corresponding unformulated (non phosphatidylcholine) curcuminoid mixture. In terms of the length of Meriva treatment, 6 weeks was chosen because it is the period of time over which we have observed a significant increase in NF-kB pathway activity related to fatigue symptoms (31).

We propose to increase the dose of Meriva 500 administered to patients randomized to the active arm of the study from 1 to 2g total per day (500mg to 1g BID, respectively). This dose increase will be implemented 1) after 10 patients have completed the protocol (5 active and 5 placebo), 2) if no statistically significant differences are noted at the primary study endpoint (peripheral blood mononuclear cell NF-kB DNA-binding) between patients randomized to the active arm and patients randomized to the placebo arm, and 3) no dose-limiting side effects have been encountered. Dose-limiting side effects are considered to be a Grade 3 (Based on NCI Common Terminology Criteria for Adverse Events) or higher adverse event that is deemed to be probably related to the drug.

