### Analytical Plan

Power analysis: Based on a preliminary data, the mean change of NF-kB DNA binding from baseline among patients who underwent six weeks XRT was 8.2 ng NF-kB per assay well (SD = 9.0). We hypothesize that in this study the patients in the placebo group will have the similar response as in the preliminary data, and patients who receive Meriva, the mean change of NF-kB DNA-binding level from baseline to 6 weeks post XRT is 0.0 with a reduced SD of 4.5. Based on alpha of 0.05 and a n = 11 per group, we will have 82% power to detect the above hypothesized difference by one-sided two-sample t test. We believe such a difference is clinically meaningful and is well within the range of differences observed in chemotherapy vs. no chemotherapy patients and fatigued vs. non-fatigued patients.

Statistical analysis plan: Primary objectives: the mean changes of NF-kB DNA binding from baseline to Week 6 will be compared between two groups using two-sample t test. The change of plasma concentration of NF-kB downstream mediators from baseline will be compared between two groups using two-sample t-test/Wilcox sum rank test for continuous measures and using Chi-square test/Fisher's exact test for categorical measures. Secondary objectives: The change of MFI over time in two groups will be compared by the GEE model.

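### Six biomarkers share primary status and are tested separately with no hierarchy, adjustment or stated level, and the sections disagree on which measures are primary

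*Combined protocol and SAP*

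**What the plan says.** The sections give different accounts of what is primary.

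- Outcome Measures makes the change in six biomarkers the primary outcome: "The primary outcome to be measured will be the change in NF-kB DNA binding and its downstream mediators". The full list is "NF-kB DNA binding and its downstream mediators (plasma concentrations of TNF-alpha, sTNFR2, IL-1ra, IL-6 and CRP) after six weeks of treatment". Its primary hypothesis also takes in gene activation and joins the parts with a conjunction: "decreased NF-kB DNA binding, decreased activation of NF-kB responsive genes and decreased downstream mediators of NF-kB pathway activation".
- Analytical Plan opens the analysis with "Primary objectives: the mean changes of NF-kB DNA binding from baseline to Week 6 will be compared between two groups using two-sample t test". It then compares the mediators between arms, also by separate two-sample tests. It gives no order of testing, no adjustment, no number of wins required, and no level or sidedness. A level of 0.05 and a one-sided test appear only in the power calculation for DNA binding.
- (iv) Design widens the set: "NF-kB DNA-binding, downstream mediators of NF-kB activity and microarray analysis of NF-kB regulated genes will be used to determine NF-kB pathway activation". The next sentence begins "If any of these measures of NF-kB DNA binding activity (the primary outcome variables" and is interrupted by a text box. It resumes to say that the dose level counts as successful if any of them falls to the mean of women who had radiotherapy without chemotherapy.
- (v) Dosing names one endpoint: "the primary study endpoint (peripheral blood mononuclear cell NF-kB DNA-binding".
- (i) Background and objectives lists four mediators: TNF-alpha, sTNFR2, and then "interleukin (IL)-1 receptor antagonist (IL-1ra), and C-reactive protein (CRP) are downstream indicators of NF-kB activity". IL-6 is not among them.

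(v) Dosing also reports that DNA binding could not be measured in the first 10 completers, because too few cells were obtained, and that power for continuing at the same dose was then judged on IL-6.

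**The concern.** With six separate primary comparisons and no rule for combining them, the analyst can report the primary objective as met on whichever marker gives a small p-value. That p-value would not reflect the number of attempts.

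The problem is a practical one here. DNA binding is the only endpoint with a power calculation in the Analytical Plan, and its assay failed in the first 10 completers. If it stays hard to measure, the trial will rest on five mediators, with no rule for choosing among them and two different lists of which ones count.

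**Working it through.** **Step 1. Reproduce the plan's figure.** Inputs from the Analytical Plan: mean change 8.2 (SD 9.0) on placebo and 0.0 (SD 4.5) on Meriva, n = 11 per group, one-sided 0.05.

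- Standard error = √((9.0² + 4.5²)/11) = √(101.25/11) = 3.034.
- Noncentrality = 8.2/3.034 = 2.703.
- Unequal-variance t test: about 14.7 degrees of freedom, critical value 1.755, power 82.4%.

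This matches the stated 82%. The two-sided version gives 71%, so the plan's figure is one-sided. It covers DNA binding only.

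**Step 2. Chance of at least one false positive among six.** Assume no true effect, a level a for each test, and one win being enough. For independent tests the chance is 1 − (1 − a)^6.

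- One-sided 0.05: 1 − 0.95^6 = 1 − 0.7351 = 26.5%.
- Two-sided 0.05, counting only wins for Meriva (a = 0.025): 1 − 0.975^6 = 1 − 0.8591 = 14.1%.

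The markers lie on one pathway, so positive correlation is likely. The documents give no correlations, so those below are assumptions. The results come from 1,000,000 draws of equally correlated normal statistics.

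| Correlation | One-sided 0.05 | Two-sided 0.05, wins for Meriva |
|---|---|---|
| 0 | 26.5% | 14.1% |
| 0.3 | 22.0% | 12.2% |
| 0.5 | 18.6% | 10.4% |
| 0.7 | 14.8% | 8.2% |
| 0.9 | 10.0% | 5.4% |
| Nominal, one test | 5% | 2.5% |

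If DNA binding is lost and only the five mediators remain, the one-sided independent figure is 1 − 0.95^5 = 22.6%. If DNA binding alone is primary, as in Dosing, the one-sided figure is 5%.

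**Step 3. Power cost of control.** Two-sided unequal-variance t test for DNA binding, difference 8.2. Enrolment of 30 per arm is from section (iii). The 25 per arm row assumes that the first 10 completers are lost, 5 per arm, which is the split Dosing gives for them. The strictest Holm step over six is 0.05/6 = 0.0083.

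| SDs | n per arm | Noncentrality | Power at 0.05 | Power at 0.05/6 |
|---|---|---|---|---|
| 9.0 and 4.5 | 30 | 8.2/√(101.25/30) = 4.46 | 99% | 95% |
| 9.0 and 4.5 | 25 | 8.2/√(101.25/25) = 4.07 | 98% | 89% |
| 9.0 and 9.0 | 30 | 8.2/√(162/30) = 3.53 | 93% | 78% |
| 9.0 and 9.0 | 25 | 8.2/√(162/25) = 3.22 | 88% | 68% |

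The rows with SD 9.0 in both arms test the plan's assumption that Meriva halves the SD. The documents give no effect sizes or SDs for the mediators, so their power cannot be computed.

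**The case against.** The best defence is that the plan does have a single primary endpoint. Dosing names DNA binding, the power calculation concerns only DNA binding, and the analysis paragraph tests it first. The primary hypothesis also joins its parts with a conjunction, which points away from one win being enough. And this is a 60-patient mechanistic study. These points show that a single-endpoint reading is available. They do not settle the matter: Outcome Measures and Design say otherwise, and the hypothesis describes patients who respond; it is not a decision rule.

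Some stronger readings are tempting and are not supported.

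- A reader might infer that the plan tests each marker at 0.05. It does not say so; the level and sidedness of the analysis are unstated.
- A reader might take the Design sentence as a rule that one significant marker is enough. It is a comparison with a reference mean and not a between-arm test, and its error rate cannot be computed from the documents.
- A reader might count gene expression as a seventh primary test. The Analytical Plan has no gene test, and the array sections define no single test statistic.
- A reader might infer that IL-6 was already examined by arm. Dosing says only that the consultation used IL-6 values from the first 10 completers. It does not say that they were split by arm.

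**Conclusion.** The concern stands as a gap in definition. Six biomarkers are primary in Outcome Measures, they are tested separately, nothing controls or ranks them, and the sections disagree on the family. As written, the primary conclusion has no stated error rate.

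The size is conditional on one win counting and on the assumed level. With six one-sided 0.05 tests the error is at most 26.5% under independence or positive correlation, about 15% at correlation 0.7 and 10% at 0.9. With two-sided tests a false win for Meriva has at most a 14% chance, or 8% at correlation 0.7, against 2.5%. A reader might quote 27% as the trial's error rate. The documents do not support that, because they fix neither the level, nor the sidedness, nor the rule for success.

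**What to change.** In Background, Design, Dosing, Outcome Measures and Analytical Plan, state one primary family, with the same mediator list throughout, and one decision rule. State the level and sidedness of the tests. Treat gene expression as secondary. Reconcile the reference-mean criterion in Design with the between-arm analysis, so that the plan has one definition of success.

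Two rules would work:

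1. Keep all six primary and test them by Holm at an overall 0.05. This leaves a valid route to a primary result if the DNA-binding assay keeps failing.
2. Make DNA binding the single primary endpoint, with the five mediators as a secondary family controlled by Holm. This is simpler and agrees with Dosing, but it rests the trial on an assay that gave no result in the first 10 completers.

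The change is to wording only and needs no extra patients. Under either rule, a mediator that wins alone at p just under 0.05 no longer meets the primary objective. Under rule 1, two-sided power for DNA binding at the strictest step falls from 99% to 95% with 30 per arm, and from 98% to 89% with 25. If both SDs are 9.0 it falls from 93% to 78% and from 88% to 68%. Further assay failures would lower it more. The cost for the mediators cannot be stated until the sponsor supplies their expected effects and SDs.
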